Opportunity to determine the impact of vitamin D and omega-3 fatty acids on stroke outcomes. The ongoing VITamin D and OmegA-3 TriaL (VITAL) (this parent study is approved by Partners IRB, Protocol #2009P001217/MGH) will examine the impact of vitamin D₃ (2,000 IU/day cholecalciferol) and omega-3 fatty acids (840 mg eicosapentaenoic acid [EPA] + docosahexaenoic acid [DHA]) on stroke incidence. Given the high morbidity burden of stroke, the impact of these supplements on stroke outcomes is of substantial scientific and public health importance. This proposal will collect additional data to determine the effect of these supplements on post-stroke outcomes. Even if they do not significantly reduce stroke incidence, they may still reduce stroke severity and improve outcomes post-stroke. The randomized doubleblind design among healthy adults will provide the highest quality data on the impact of these agents on long-term stroke outcomes.

II. Specific Aims

The primary specific aim of this study is to test whether vitamin D₃ or omega-3 fatty acid supplementation reduces the risk of poor functional outcomes as measured at hospital discharge and 6- and 12-months post-stroke (~400 strokes in VITAL).

III. Subject Selection

Participants will be selected from the VITAL study. VITAL is a NIH-funded (CA138962 with support also included from NHLBI) randomized, double-blind, placebo-controlled trial to test the effects of vitamin D₃ (cholecalciferol, 2,000 IU/d) and omega-3 fatty acid (840 mg/d of EPA/DHA [ratio of 1.3:1]) supplements in the primary prevention of CVD and cancer in a multiethnic population of 25,875 individuals.¹⁸ The trial enrolled men aged \geq 50 and women aged \geq 55 without a history of cancer (except non-melanoma skin cancer), myocardial infarction, stroke, transient ischemic attack, or coronary revascularization. All subjects signed a detailed informed consent form, agreed to limit consumption of supplemental vitamin D and calcium to no more than 800 IU/d and 1200 mg/d respectively and to forgo use of fish-oil supplements during the trial. This ongoing parent study is approved by Partners IRB, Protocol #2009P001217/MGH. Additionally, VITAL received IND approval from the FDA on March 11, 2011 (IND #105558) and is registered on clinicaltrials.gov (NCT01169259).

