Our specific aim examines the influence of randomized treatment assignment on risk of functional outcomes from stroke at 6 and 12-months after stroke. For this component, we will include only individuals in VITAL who experienced a stroke event.

IV. Subject Enrollment

For the VITAL participants who report a stroke event, at 6 and 12-months after their reported stroke event, we will invite them to complete an additional questionnaire asking about their current limitations in everyday activities. For non-responders, a second request will be made. Consent to participate will be implied by completing the questionnaire.

V. Study Procedures

Stroke Outcomes Assessment in VITAL

The parent VITAL trial collects information on stroke severity at hospital discharge as measured by the modified Rankin scale (mRS). We will send additional follow-up questionnaires at 6months and 12-months post-stroke to assess stroke outcomes for all participants who experience a stroke. This information is not collected by the parent study and will only be collected by this study. Assessing outcomes at 6 and 12-months will allow us to determine initial stroke recovery as well as further improvements or sustained functioning. The stroke outcome questionnaires will include the same functional assessment questions as the baseline questionnaire in the parent study to allow for comparisons to baseline functional status. These questions assessed baseline physical function and limitations in: vigorous or moderate activities; lifting or carrying groceries; climbing stairs; bending, kneeling, stooping; walking >1 mile; walking several blocks; or walking 1 block. Respondents are also asked if they received help with feeding themselves, dressing, getting in and out of bed, and taking a bath or shower.

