In addition, I will ask several questions originally developed and used by the Framingham Heart Study (FHS) to assess functional limitations, physical disability, and social disability among individuals with stroke.^{19, 20} Functional limitations will be assessed through the physical performance scale adapted from Nagi²¹ and physical disability with the modified Katz Activities of Daily Living (ADL) Scale²² and the Rosow-Breslau Functional Health Scale.²³ These measures have high test-retest reliability.²⁴⁻²⁹ The adapted Nagi scale asks respondents if they experience limitations in: pulling or pushing large objects; stooping, crouching, or kneeling; reaching or extending arms above shoulder level; reaching or extending arms below shoulder level; writing or handling or fingering small objects; standing in one place for long periods; and sitting for an hour. The Rosow-Breslau Functional Health Scale asks if the respondent needs help with the following gross mobility tasks: walking 0.5 mile; walking up and down stairs to the second floor; and doing heavy work around the house. The modified Katz ADL scale asks about needing help with: bathing; dressing; eating; getting in and out of a chair; and walking 50 yards. I will also ask participants if they are completing the questionnaire themselves or if it has been completed by a proxy respondent and if they currently reside in a nursing home. I will create cumulative disability scales similar to those previously developed in stroke survivors in FHS.¹⁹ First, I will dichotomize responses to each item as unlimited (no limitation or no help needed) versus limited (any amount of limitation or help needed). Next, each scale (Nagi, Katz, and Rosow-Breslau) will be dichotomized into unlimited (no limitation in any of the items) versus limited (limitation in at least one item). Finally, I will create a cumulative disability index with values of 0 (no limitation on any scale), 1 (limitation on Nagi scale only), 2 (limitations on Nagi and Rosow-Breslau scales), and 3 (limitations in all three scales).

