Social disability will be assessed using a scale also developed in the FHS²⁰ which incorporates both need for assistance and unmet need for assistance. Someone with a need for assistance is not self-sufficient in performing the activity, but is able to find support to meet this need. In contrast, those with an unmet need are not able to find this support. The scale covers five social areas (housekeeping, transportation, social interaction, food preparation, and grocery shopping). Respondents are grouped into four categories (need met, no apparent problem; need met, potential problem; uncertain need met, potential problem; need unmet, current problem) for each social area using a previously published algorithm.²⁰ I will examine each social area individually and create summary indices for the total number of unmet needs across all areas and for the total number of unmet needs or uncertain needs met, potential problem. These indices range from 0 to 5, but to avoid problems with model convergence due to sparse data I will *a priori* categorize them as 0, 1, or ≥ 2 .

VI. Biostatistical Analysis

We will use logistic regression to examine the effects of randomized treatment assignments in VITAL on functional limitations, physical disability, and social disability using separate models

for each outcome as defined above. Only individuals with a completed stroke outcomes questionnaire will contribute to these analyses. We will perform analyses for total stroke as well as for the ischemic strokes only. For the analysis of functional limitations and physical disability, we will also perform a sensitivity analysis in which we restricted to those individuals who did not report functional limitations at baseline in VITAL.

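### The primary aim is a test, but 11 questionnaire outcomes per agent are modelled separately and no outcome or time point is named to decide it

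*Combined protocol and SAP*

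**What the plan says.** Section II (Specific Aims) gives a single primary aim, "to test whether vitamin D₃ or omega-3 fatty acid supplementation reduces the risk of poor functional outcomes". The aim covers three assessment points (discharge, 6 months and 12 months) and expects about 400 strokes. Section III (Subject Selection) restates it without hospital discharge, as concerning "risk of functional outcomes from stroke at 6 and 12-months after stroke".

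Section V (Study Procedures) defines the questionnaire outcomes:

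- For physical function, "each scale (Nagi, Katz, and Rosow-Breslau) will be dichotomized into unlimited (no limitation in any of the items) versus limited". A cumulative disability index with values 0 to 3 is then built from these three scales.
- For social disability there are five areas, each sorted into four categories, and two counts over the areas: "I will examine each social area individually and create summary indices". Each count is grouped as 0, 1, or 2 and above.

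Section VI (Biostatistical Analysis) applies logistic regression to "functional limitations, physical disability, and social disability using separate models", one for each outcome defined earlier. It adds: "We will perform analyses for total stroke as well as for the ischemic strokes only". The analyses restricted to participants unlimited at baseline, with propensity weights, and with fatal strokes as the worst category are labelled sensitivity analyses. The main outcomes carry no ranking. The document gives no primary outcome, lead time point, significance level, testing order or multiplicity rule, and does not call the results exploratory.

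**The concern.** A primary aim worded as a test calls for a result that answers it. Here, if one scale at 6 months is nominally significant and the remaining outcomes are not, the plan does not say whether the aim has been met. Any of the separate results could be put forward after the data are seen, and a mixed pattern has no interpretation fixed in advance.

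The study expects about 400 strokes, and only those who complete a questionnaire enter the main models. Isolated nominal findings are therefore quite possible by chance, and a reader could not tell such a finding from a planned answer to the aim.

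**Working it through.** The plan states no error rate, so there is no figure of its own to reproduce.

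**Count of tests**

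- Outcomes (Section V): 3 scales + 1 cumulative index + 5 social areas + 2 social indices = 11.
- Times (Sections II to V): 6 and 12 months, so 11 × 2 = 22 tests per agent. Separate modelling of the two times is inferred, because Section VI does not state it. If only one time is tested, there are 11.
- Not counted: the modified Rankin scale at discharge, the ischemic-only repeats and the sensitivity analyses.

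**Assumptions, because the plan gives no values:** two-sided 5% per test (critical value c = 1.96), no treatment effect, and a common correlation ρ between test statistics.

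**Formulas, m tests**

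- Independent tests: 1 − 0.95^m. For m = 22 this is 0.676; for m = 11 it is 0.431. The expected number of false positives with 22 tests is 22 × 0.05 = 1.1.
- Equal correlation ρ, either direction: 1 − ∫ φ(u) [Φ((c − √ρ u)/√(1−ρ)) − Φ((−c − √ρ u)/√(1−ρ))]^m du.
- Favourable direction only: 1 − ∫ φ(u) [Φ((c − √ρ u)/√(1−ρ))]^m du. A single test gives 2.5%.

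**Chance of at least one nominally significant result, per agent, total stroke**

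| ρ | 22 tests, either direction | 11 tests, either direction | 22 tests, favourable only |
|---|---|---|---|
| 0 | 68% | 43% | 43% |
| 0.3 | 57% | 38% (0.375) | 30% |
| 0.5 | 44% | 30% | 22% |
| 0.7 | 30% | 22% | 15% |
| 0.8 | 23% | 18% | 12% |
| 0.9 | 16% | 13% | 8% |

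**Why the ρ = 0 row is only a bound.** The cumulative index is a function of the three scales. Both social indices count over the same five areas, and the second includes the first. Both time points come from the same people. The tests are therefore positively dependent by construction.

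**Checks on the equal-correlation model, 22 tests, either direction**

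- With separate correlations between outcomes and between times, the chance is 58% (outcomes 0.3, times 0.5), 46% (0.5, 0.7) and 34% (0.7, 0.7).
- All 11 outcomes were also simulated at two times from a shared latent disability, with 200 or 300 respondents and assumed prevalences. This gave 26% to 59% as the sharing went from near-complete to weak. The error of an individual test stayed at about 4.5% to 5.0%, so sparse categories do not remove the excess.

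**Can the cumulative index serve as a lead outcome as it stands?** Three dichotomised scales give 2³ = 8 response patterns. Section V assigns values to four: none, Nagi only, Nagi plus Rosow-Breslau, and all three. Four patterns have no value: Rosow-Breslau only, Katz only, Nagi plus Katz, and Rosow-Breslau plus Katz.

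**The case against.** The strongest reply is that the plan sets no significance level and no decision rule. Section VI speaks of examining effects and estimating associations, and in an add-on questionnaire study of about 400 strokes, separate labelled estimates with intervals are a legitimate choice. That stands as a choice, but the document does not make it. The aim is called primary and is framed as a test, and the Summary says the data will settle whether supplementation reduces poor outcomes.

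Several objections to the size also stand:

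- **Fixed range.** A reader might infer that the plan carries a false-positive chance of 30-68% per agent. The documents do not support that as a property of the plan. The 5% level is assumed, 68% needs an independence that the overlapping outcomes rule out, and 30% is no floor because higher correlation goes below it.
- **Direction.** The aim concerns a reduction in risk. A significant result in the harmful direction would not support it, so the favourable-only column is the more relevant one for a false claim of benefit.
- **The count.** Besides the inference about two time points, the three dichotomised scales could be read as mere steps towards the index. That leaves 1 + 5 + 2 = 8 outcomes, or 16 tests at two times, which falls between the 11- and 22-test columns.
- **Both agents together.** Squaring the per-agent chance of no false positive gives figures up to 90% across agents. This needs the two agents' tests to be independent, and the document does not describe a factorial allocation, so the point does not rest on it.

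**Conclusion.** The point holds: the plan as written gives no single answer to its primary aim, because no outcome or time point is designated to decide it. That conclusion needs no numerical assumption.

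The size does need assumptions. At two-sided 5% per test and correlations of 0.3 to 0.9, the per-agent chance of at least one nominally significant result under no effect is about 16-57% with 22 tests, or about 13-38% with 11. For favourable results alone it is about 8-30% with 22 tests, against 2.5% for one. Every value is well above that of a single test, and the ischemic-only repeats and discharge outcome can only add to it. The finding does not show that a false claim would be made. It shows that nothing in the plan prevents an isolated result from being read as the answer.

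**What to change.** For each agent, name one primary test in total stroke at one time point. One workable choice is the cumulative disability index at 12 months, by proportional-odds logistic regression with a stated significance level. Nothing in the documents favours this outcome over the others, so the choice is the investigator's, provided it is made before the results are seen.

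If the index is chosen, redefine it first so that all eight response patterns have a value, for example the number of the three scales with any limitation, 0 to 3. Specify the ordinal model as well, since Section VI says only logistic regression.

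Report all other outcomes, the other time point, the modified Rankin scale at discharge and the ischemic-only results as secondary or supportive estimates with 95% intervals. State that none of them can establish the aim on its own. State also whether 6 and 12 months are modelled separately.

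The cost is changed text and a small amount of analysis work to define the index coding and the ordinal model. No new data are needed. The downside is that an isolated significant secondary outcome can no longer support a claim.

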Recently, there is growing interest in the effect of vitamin D and omega-3 fatty acids on cardiovascular disease risk. A recent meta-analysis of observational studies found that individuals with the lowest serum 25-hydroxyvitamin D (25(OH)D) levels had a relative risk of 1.64 (1.27-2.10) for stroke compared to those with the highest levels.³ In contrast, a meta-analysis of randomized trials of vitamin D supplementation did not find an effect on stroke risk (RR=1.05)⁴; however, the levels of supplementation tested in the trials were low.⁵ Omega-3 fatty acid intake was associated with reduced risk of stroke among healthy individuals in a meta-analysis of observational studies.⁶ No published large randomized trials of marine omega-3 fatty acids for the primary prevention of CVD in the general population exist. Randomized trials of omega-3 fatty acid supplementation among patients with cardiovascular disease (CVD)^{7, 8}, hypercholesterolemia⁹, or dysglycemia¹⁰ observed no effect on stroke risk.

Impact of vitamin D and omega-3 fatty acids on stroke outcomes: Gaps in knowledge. Information on the effect of vitamin D and omega-3 fatty acid supplementation on stroke outcomes (as opposed to incident stroke) in healthy populations is limited. Studies among stroke patients observed that lower levels of 25(OH)D at hospital admission predict infarct volume¹¹, initial stroke severity and handicap at hospital discharge¹², as well as death and functional outcome at 90 days post-stroke.¹³ However, these studies cannot test if supplementation with vitamin D in healthy populations impacts stroke severity and functional outcomes post-stroke. Several hypotheses have been formulated to explain how vitamin D may impact stroke outcomes. Vitamin D may have neuroprotective properties¹⁴ and 25(OH)D may promote neuroplastic changes which improve recovery after stroke.¹² Additionally by preserving bone, restoring muscle strength, reducing falls, and protecting against cognitive impairment and depression, vitamin D may assist in post-stroke recovery.^{15, 16} Less is known about the impact of omega-3 fatty acid supplementation on stroke outcomes. An animal study observed that a DHAenriched diet protected against post-ischemic inflammation and injury in the brain.¹⁷ This suggests that DHA may protect against the immune response or brain damage in ischemic stroke and may result in improved stroke outcomes.

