We will also perform a sensitivity analysis in which we will use inverse probability of treatment weights to adjust for potential differences between treatment groups since our analysis conditions on experiencing a stroke event. We will first develop a propensity score for randomized treatment assignment at the time of stroke including information on age at randomization, sex, body mass index, physical activity, statin use, alcohol consumption, history of hypertension, history of high cholesterol, race, and smoking status to predict treatment assignment. We will then use weighted logistic regression to estimate the association between randomized treatment and our outcomes. We will perform an additional sensitivity analysis in which fatal stroke events were included as the worst possible outcome category.

References

McKay J, Mensah GA. Atlas of Heart Disease and Stroke: World Health Organization;
2004.

7. Dietary supplementation with n-3 polyunsaturated fatty acids and vitamin E after myocardial infarction: results of the GISSI-Prevenzione trial. Gruppo Italiano per lo Studio della Sopravvivenza nell'Infarto miocardico. Lancet. 1999;354(9177):447-55.

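### Every planned comparison is made among stroke cases only; the weighting is a partial answer, and no analysis in this plan compares the groups as randomised

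*Combined protocol and SAP*

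**What the plan says.** Section III sets the analysis population: "For this component, we will include only individuals in VITAL who experienced a stroke event". Section VI narrows the main logistic models further: "Only individuals with a completed stroke outcomes questionnaire will contribute to these analyses".

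Section VI then lists the variations: ischaemic strokes only; a restriction, for functional limitation and physical disability, to people without limitations at baseline; inverse probability of treatment weighting; and a fatal-stroke analysis ("We will perform an additional sensitivity analysis in which fatal stroke events were included as the worst possible outcome category"). The weighting is a sensitivity analysis, and its stated purpose is to "adjust for potential differences between treatment groups since our analysis conditions on experiencing a stroke event".

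Section I treats stroke incidence as a parent-trial question and leaves its answer open: "Even if they do not significantly reduce stroke incidence, they may still reduce stroke severity and improve outcomes post-stroke". It also presents the randomised design as the guarantee of quality for these outcome data.

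The aim in Section II is whether either agent "reduces the risk of poor functional outcomes as measured at hospital discharge and 6- and 12-months post-stroke". Section V says the parent trial collects the modified Rankin scale (mRS) at discharge. Section VI names functional limitations, physical disability and social disability, and has no mRS model.

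**The concern.** Randomisation balances the 25,875 people enrolled. It does not by itself balance the roughly 400 who go on to have a stroke if treatment influences who they are. If an agent prevents strokes with a good prognosis, the remaining strokes in that arm look worse and the agent appears harmful after stroke. If it prevents strokes with a poor prognosis, it appears beneficial. Either can happen with no effect on recovery.

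The planned weights balance what they contain, in so far as the propensity model is right. They do not balance an unmeasured cause of both stroke and poor outcome, and they do not address who returns a questionnaire. The no-baseline-limitation and fatal-as-worst analyses change the set of strokes or the outcome coding, but both stay within strokes.

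What is at stake is the description of the result. A stroke-only odds ratio could be reported as a randomised effect on stroke outcome, with nothing beside it to show how many strokes, or disabling strokes, each arm had.

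**Working it through.** **Scope.** The total-stroke, ischaemic-only, no-baseline-limitation, weighted and fatal-as-worst analyses were checked in turn; none uses all randomised participants. The propensity covariates are age, sex, body mass index, physical activity, statin use, alcohol, hypertension, high cholesterol, race and smoking: ten. Expected strokes are 400/25,875 = 1.5%. Under 1:1 allocation (assumed) that is about 200 strokes per arm of about 12,938. The plan gives no power or bias figure to reproduce. All risks and prevention rates below are assumptions.

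**Illustration 1: selection on severity.** Control arm: 100 milder and 100 severe strokes, with limitation risk 0.3 and 0.8. Treatment prevents 20% of the milder strokes and has no effect on outcome.

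- Control: limited 30 + 80 = 110, unlimited 90.
- Treated (80 milder, 100 severe): limited 24 + 80 = 104, unlimited 76.
- OR = (104 × 90)/(76 × 110) = 9,360/8,360 = 1.12.
- SE of log OR = √(1/104 + 1/76 + 1/110 + 1/90) = 0.207, so the 95% CI is 0.75 to 1.68.
- As randomised, with SE = √(1/a − 1/n + 1/c − 1/n) and n = 12,938: any stroke 180/200 = 0.90 (0.74 to 1.10); stroke with limitation 104/110 = 0.95 (0.72 to 1.24).

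Equal 20% prevention in both strata gives 88/72 against 110/90, OR 1.00: no bias. With 10% to 30% prevention in one stratum and limitation risks 0.4/0.7 or 0.3/0.8, the spurious OR runs from 1.03 to 1.20 (milder prevented) or 0.97 to 0.84 (severe prevented).

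**At the cited incidence ratio.** Section I gives RR 1.05 for vitamin D, so 200 × 1.05 = 210 strokes. If all ten extra strokes are milder: 113/97 against 110/90, OR 0.95 (0.65 to 1.41). If all are severe: 118/92 against 110/90, OR 1.05 (0.71 to 1.55).

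**Illustration 2: an unmeasured common cause U.** Illustration 1 selects on a feature of the stroke itself, so it does not represent this mechanism. Assume U has prevalence 0.3, doubles stroke risk and is unrelated to the ten covariates. Poor-outcome risk is 0.4 without U, and the odds ratio for U is 2 to 5. With treatment's stroke RR t0 (U absent) and t1 (U present), the share of strokes with U is q = 0.6·t1/(0.6·t1 + 0.7·t0).

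- Control: 0.6/1.3 = 0.462.
- t0 = 0.6, t1 = 1: q = 0.6/1.02 = 0.588. With odds ratio 5, outcome risk is 0.617 against 0.570, OR 1.21; with odds ratio 2, OR 1.09.
- t0 = 1, t1 = 0.6: q = 0.36/1.06 = 0.340, OR 0.92 to 0.83.
- t0 = 1.2, t1 = 0.8: overall stroke RR (0.84 + 0.48)/1.3 = 1.02, yet OR 0.935 to 0.864.

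The middle two cases need 40% prevention confined to one stratum. The last shows that near-null net incidence does not exclude selection.

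**Against sampling error.** With 400 strokes, 60% to 100% response and control risk 0.3 to 0.7 (assumed), the OR detectable with 80% power at two-sided 5% is about 0.41 to 0.57. Every spurious OR above is closer to 1.

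**Precision of an all-randomised companion.** With 100 control events and a true ratio of 0.8, z = (100 − 80)/√(100 + 80) = 1.49, and power = Φ(1.49 − 1.96) = 32%.

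**Missing questionnaires.** In Illustration 1 at 75% response (assumed; no rate is given), respondents with limitation are 78 and 82.5, and missing are 45 and 50. All missing poor: 123/132.5 = 0.93. None poor: 78/82.5 = 0.95. Opposite directions by arm: 78/132.5 = 0.59 and 123/82.5 = 1.49. The same-direction pair therefore does not cover differential non-response.

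**The case against.** The plan states the conditioning openly and pre-specifies a response. Its question is about outcome after a stroke, which is conditional by nature. Stroke incidence belongs to the parent trial, whose own plan is not available here. The randomised evidence in Section I shows no effect on stroke: RR 1.05 for vitamin D, and none for omega-3 in higher-risk patients. An all-randomised endpoint mixes incidence with recovery, is imprecise, and cannot prove or exclude selection. Adding many estimates could confuse more than it clarifies.

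Most of this stands, and it sets the size of the point. It does not remove it: Section I itself says the vitamin D trials used low doses and that no large omega-3 primary-prevention trial had been published, and an overall null is not enough, as Illustration 2 shows.

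A reader might go further than the documents allow in three ways:

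- That the stroke-only odds ratios are biased. This is not shown; the bias is zero if treatment leaves the mix of strokes unchanged in prognosis.
- That any imbalance survives the weighting. Selection acting only through a weighting covariate, such as age, is removed by a correctly specified propensity model, and the OR returns to 1.00.
- That the missing discharge model is evidence of selection. It is a separate mismatch between aim and analysis.

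**Conclusion.** The concern holds as a matter of interpretation and reporting, and it is worth a cheap improvement. All planned analyses condition on a post-randomisation event, the main models condition again on response, and the one analysis aimed at the conditioning handles only ten measured covariates. The plan contains no comparison as randomised and no model for the discharge outcome in its own aim.

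The likely size is small. The spurious OR is about 1.12 under the 20% milder-prevention assumption and 0.95 to 1.05 at the cited incidence ratio, against a 95% interval of roughly 0.75 to 1.68. These figures rest on assumed risks, 1:1 arms and about 200 control strokes. They illustrate what selection could do; they do not estimate what it did.

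**What to change.** Keep the planned analyses and add to Section VI, as supplementary:

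1. *For each agent, all randomised participants will be compared as assigned on (a) stroke with limitation at 6 and at 12 months, separately on the Nagi, Rosow-Breslau and Katz scales, and (b) stroke with at least one unmet social need at 6 and at 12 months. Fatal stroke counts as a poor outcome. No stroke, or stroke with a better outcome, counts as no event. Death from another cause before the assessment will be counted as [to be stated]. Missing questionnaires will be counted as all poor, then as all not poor, in both arms.*
2. *Discharge mRS, at a cut fixed before the treatment comparison is seen, will be modelled among stroke cases and in all randomised participants.*
3. *Stroke incidence by arm with 95% confidence intervals, and baseline covariates by arm among strokes and among completers, will be shown beside the stroke-only estimates.*
4. *Stroke-only estimates are conditional on having a stroke and are not fully protected by randomisation.*

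Item 1 uses the plan's own coding, in which "each scale (Nagi, Katz, and Rosow-Breslau) will be dichotomized into unlimited (no limitation in any of the items) versus limited", and should be set beside the planned fatal-as-worst analysis. The text should acknowledge that its missing-data bounds do not cover non-response that differs by arm. Attach no decision rule: the stroke-only and all-randomised estimates share the same poor-outcome strokes, so agreement in direction is not confirmation.

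Cost: SAP wording and analysis time. Per agent there are nine all-randomised comparisons (three scales at two times, social need at two times, mRS once), one stroke-only mRS model and two tables. The data are already collected by the parent trial or this study, so no new participant contact is needed. The downside is an imprecise answer to a related question, the risk of disabling stroke, which is why it supplements and does not replace the planned analysis.
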